Screening: Subjects who satisfy eligibility criteria may be entered into the study. Subjects must have sufficient historical data on renal function to allow for determination of the rate of progression of renal disease prior to injection (Inclusion Criterion 8). Screening procedures will include a full physical examination, electrocardiogram, and laboratory assessments (hematology, serum chemistry, and urinalysis). In addition, an MRI will be performed to assess kidney volume using site standard practices.

Biopsy: Patients not previously enrolled in a Phase 1 trial will require a renal biopsy to obtain the cells for injection. The biopsy specimens obtained from patients previously enrolled in a Phase 1 trial and maintained in a frozen state will be used to generate the second quantum of NKA to be injected under this protocol, if sufficient cells are available after thawing. If the number of cells obtained after thawing the frozen biopsy specimens is insufficient, the patient may need to have an additional biopsy procedure completed for this study.

Injection: Ten to 14 days before the scheduled injection date, subjects will report to the clinic for verification of final eligibility criteria. In addition, a renal scintigraphy study will be performed to obtain a baseline assessment of split kidney function. Subjects who meet appropriate I/E criteria will

be admitted to the hospital/clinical research unit early in the morning on the day of scheduled injection (Day 0). NKA will be injected into the biopsied kidney, using one of two available options: (1) a laparoscopic approach; or (2) a percutaneous approach. The laparoscopic method may utilize robotic assistance to stabilize the kidney while the injection is performed with laparoscopic viewing; while the percutaneous method will employ a standardized technique such as utilized in the ablation of renal masses by radiofrequency or cryogenic methods. Subjects will remain hospitalized for a minimum of 2 nights and up to 4 nights following a laparoscopic injection (or until any procedure- or product-related AE's have resolved or stabilized). Patients may be discharged the same day following a percutaneous injection without complications. An ultrasound study will be performed on Day 1 to verify the lack of subclinical adverse effects for both approaches.

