Ten to 14 days before the scheduled injection, the patient should report to the clinic for a preinjection qualification visit including final review of I/E criteria and a renal scintigraphy study. If the patient is still eligible for injection, the site will notify Twin City Bio LLC to manufacture NKA product from frozen renal cells. On the day of injection (Day 0), the patient should be admitted to the hospital and receive an NKA injection into the left (i.e., biopsied) kidney. For injection, the kidney will be accessed either (a) laparoscopic approach, or (b) using a percutaneous approach. The patient will remain in the hospital for two to four nights following the laparoscopic procedure, or 0-1 night following the percutaneous procedure, for observation and safety assessments. The patient should not be discharged until any procedure- and/or product-related AE's which may have occurred have stabilized or resolved.

Post-injection Follow-up: Subjects will return to the clinic for follow-up safety assessments on Days 7, 14, and 28 post-injection and at 3, 6, 9, and 12 months post-injection. At 6 months post-injection, post-treatment MRI and renal scintigraphy studies will be conducted. After patients complete the 6 month efficacy visit, they will be considered for a second NKA injection. Patients receiving a second dose will follow the same follow up visits that occurred after first dose. Patients 6 month post first injection visit will serve as the patients 14 to 10 day pre- second injection visit. Patients will return for their second injection and at 2, 3, and 6 months post-second injection. Patients will be followed up to 18 months in the post follow up phase with 6 months after first NKA injection and 12 months after second NKA injection. Refer to the time and events schedule on page 14 for additional post follow up time points. Subjects will complete an End-of-Study visit when they discontinue from the study or (for those who complete the study) at 18 months post-second injection.

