12.3 Laboratory Assessments

Laboratory assessments are listed below in Table 8. All samples will be collected as shown in the Time and Events Schedule: Laboratory Assessments will be assayed at a central laboratory designated by RegenMed (Cayman) Ltd. Laboratory results will be graded using the NCI CTCAE grading scale.

Chemistry	Hematology		
Standard Panel	Hemoglobin - Hb		
Alanine Aminotransferase: ALT	Hematocrit - HCT		
Alkaline Phosphatase: ALP	Platelets		
Aspartate Aminotransferase: AST	RBC Count		
Bilirubin	WBC Count		
Creatine Kinase: CK	WBC Differential		
Gamma-glutamyl Transferase: GGT	Coagulation Status		
Lactate Dehydrogenase: LDH	Activated Partial Thromboplastin Time: APTT		
Renal Analytes	INR		
Albumin, serum			
Calcium, serum	Urine Chemistry		
CO2, total	Protein & Albumin		
Creatinine, serum	Creatinine		
Cystatin-C	Protein & Albumin:Creatinine Ratio (PCR & ACR)		
C Reactive Protein: CRP	NeutroPhase 11 Gelatinase-associated Lipocalin		
	(NGAL)		
Glucose, serum	Routine Urinalysis: UA*		
Phosphorus, serum	Additional Selected Analytes		
Potassium, serum	ß2-Microglobulin, serum & urine		
Sodium, serum	Hemoglobin (Hb) A1c		
BUN	(intact) Parathyroid hormone; PTH		
	Virology		
Lipid Panel	HIV-1, HBV, HCV		
Cholesterol			
LDL	Research (Reserve) Analytes		
HDL	Serum/plasma and urine sample		
LDL:HDL ratio	Example: Fibroblast Growth Factor 23, Pentaxin 3		
Triglycerides	Pregnancy (urine)		
*Routine UA using a urine test strip (dipstick). M	ficroscopic analysis should only be performed if albumin,		

Table 8: Laboratory Assessments

*Routine UA using a urine test strip (dipstick). Microscopic analysis should only be performed if albumin, leukocytes, erythrocytes, or nitrites are positive.

eGFR: For comparison of all subjects across the study, GFR will be estimated using the CKD-EPI equation. The specific assay for measuring creatinine will be defined by RegenMed (Cayman) Ltd. and the samples will be analyzed by the central laboratory. For comparison to each subject's historical values, it may be necessary to perform a second analysis at the site laboratory used to generate the historical data.

Virology: The biopsy samples collected from the patients will be used for selection of SRC and manufacture of NKA. Therefore, the patient will be tested for viral blood-borne pathogens including HIV, HBV, and HCV.

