12.4.3 Renal Scintigraphy

Renal scintigraphy has been used for a long time to measure relative kidney function. Historically, the method was performed with different radiopharmaceuticals such as dimercaptosuccinic acid labeled with Technetium-99m (99mTc-DMSA), diethylenetriamine pentaacetic acid (99mTc-DTPA), mercaptoacetyltriglycine (99mTc-MAG3), ethylenedicysteine (99mTc-EC) and orthoiodohippurate labeled with 131-J (131J-OIH). Among these, 99mTc-DMSA, a static renal agent, is considered as the most reliable method to measure relative renal function and is the preferred agent for this study.

Renal scintigraphy using 99mTc-DMSA is being advocated as the preferred method for assessment of renal function following several types of kidney disease. Its uptake correlates with effective renal plasma flow, glomerular filtration rate and creatinine clearance. Its quantitative measurement is therefore a good index for relative renal function. Previous studies have shown

that 99mTc-DMSA uptake differentiates normal from diseased kidney. If the site routinely uses a different agent, then the method should be reviewed at the site initiation visit.

The site should use their standard site procedure. Outline of an example procedure is below:

- Patient should receive an intravenous injection of 50MBq 99mTc-DMSA with imaging performed 3 hours after injection.
- Patient will be placed in supine position and an acquisition of posterior view with preset time of 15 minutes, 256x256 matrix will be performed with ultra- high resolution collimator.
- Differential renal function will be calculated using region-of-interest drawings.

Note: If site standard practice is to use a labeled agent other than 99mTc-DMSA, then the site must discuss the procedure with RegenMed (Cayman) Ltd. staff prior to site initiation. If the procedure is considered sufficiently equivalent to the procedure listed in the protocol, then the site will be allowed to use their standard procedure. In this case, the procedure will be signed by the RegenMed (Cayman) Ltd. Project Leader and a copy kept in the site's regulatory binder.

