14.3 Endpoints

The primary endpoint of the study is to assess the safety and efficacy of NKA injected in one recipient kidney and determine if two injections of NKA provide stabilization of renal function.

- Primary Safety Outcome Measures: procedure and/or product related adverse events (AE's) through 12 months following the initial NKA injection.
- Primary Efficacy Outcome Measures: serial measurement of serum creatinine and estimation of GFR through 6 months following the second cell injection

Secondary Endpoint

The secondary endpoint of the study is to assess the safety and tolerability of NKA administration by assessing renal-specific adverse events over a 12 month period following a patient's first NKA injection.

• Secondary Safety and Tolerability Outcome Measures: renal-specific laboratory assessments through 12 months following the last NKA injection under this protocol, whether first or second.

Exploratory Endpoints

The exploratory endpoint of the study are designed to assess the impact of NKA on renal function over a 12 month period following the initial NKA injection.

• Exploratory Outcome Measures: clinical diagnostic and laboratory assessments of renal structure and function (including eGFR, serum creatinine, and proteinuria) to assess changes in the rate of progression of renal disease; and effect of method of injection on these parameters.

Exploratory quality of life outcome measure will be the Kidney Disease Quality of Life survey obtained at baseline and at 1, 3, 6, 7, 9, 12, 15, 18, 30, and 42 months after a patient's first NKA injection.

- Changes from baseline in BUN, $_{\beta}2$ microglobulin and intact parathyroid hormone (iPTH) at 6 and 12 months post-injection.
- Changes from baseline in C-reactive protein (CRP) at 6 and 12 months post-injection.
- Need for initiation of renal replacement therapy.
- Comparison of pre-injection versus post-injection split functional differences between the left and right kidney based on renal scintigraphy.
- Comparison of pre-injection and post-injection kidney volume estimates based on comparative MRI assessments.
- Subgroup analyses will compare patients receiving a single injection with patients receiving two injections, and patients receiving laparoscopic injections with patients receiving percutaneous injections.

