14.7.4 Other Safety Evaluations

Data from ECG, physical exam, medical history, concomitant medication, vital signs, ultrasound, renal scintigraphy, and MRI assessments will be provided in a data listing. Descriptive statistics for these evaluations will be generated as warranted.

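### The exploratory scintigraphy endpoint uses relative split function only, so a rise in the injected kidney's share cannot be told from a faster fall in the other kidney

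*Combined protocol and SAP*

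**What the plan says.** Sections 7.2, 14.2 and 14.3 define the endpoint in the same terms: "Comparison of pre-injection versus post-injection split functional differences between the left and right kidney based on renal scintigraphy". Section 12.4.3 presents the scan as a relative measure: "Renal scintigraphy has been used for a long time to measure relative kidney function", and of the preferred tracer's uptake, "Its quantitative measurement is therefore a good index for relative renal function". The only quantity derived in its example procedure is a split: "Differential renal function will be calculated using region-of-interest drawings". The synopsis gives the baseline scan the same purpose: "a renal scintigraphy study will be performed to obtain a baseline assessment of split kidney function".

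On timing, Section 9 says "At 6 months post-injection, post-treatment MRI and renal scintigraphy studies will be conducted". The Time and Events Schedules also mark scintigraphy at Months 12 and 18, and the laboratory schedule in Section 4 marks the renal panel at each of these visits. Total function is handled separately in Section 12.3: "For comparison of all subjects across the study, GFR will be estimated using the CKD-EPI equation".

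For analysis, Section 14.6 is marked as not applicable. Section 14.7.4 places scintigraphy in a data listing and adds "Descriptive statistics for these evaluations will be generated as warranted". Neither there nor in Sections 14.3 and 14.8 is the split combined with eGFR or turned into a per-kidney value.

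**The concern.** One kidney is injected in a progressive disease that affects both. The injected kidney's share therefore rises if that kidney improves, if it holds while the other declines, or if both decline and the other does so faster. A sponsor would read these three results very differently, but the endpoint as defined records them identically.

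This matters more than it would in a controlled trial. The study has a single group, and the comparator is each patient's own history. Scintigraphy is the only planned functional measure that observes the uninjected kidney over the same period. Recoding left/right as injected/uninjected is needed, because Section 6.5.3 lets new patients be treated on either side, but recoding alone does not remove the ambiguity.

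**Working it through.** The documents give no effect size, standard deviation or expected shift for this endpoint, so there is no stated figure to reproduce.

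**Identity.** Let I be the injected kidney, C the other, T = I + C and s = I/T. The share alone gives only I/C = s/(1 − s). With T known, I = s × T and C = (1 − s) × T.

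**Illustrative inputs.** T = 35 is the midpoint of the 20 to 50 entry range for new patients. The 50/50 start (17.5 + 17.5) and the move to 55% are assumptions.

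- Case A, injected rises, other unchanged: I = 0.55/0.45 × 17.5 = 21.4.
- Case B, injected unchanged, other falls: C = 0.45/0.55 × 17.5 = 14.3.
- Case C, both fall, with T down 20% to 28.0: I = 0.55 × 28 = 15.4; C = 0.45 × 28 = 12.6.

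| Case | I | C | T | Share | Change in I | Change in C | Difference of changes |
|---|---|---|---|---|---|---|---|
| A | 21.4 | 17.5 | 38.9 | 55% | +3.9 | 0.0 | +3.9 |
| B | 17.5 | 14.3 | 31.8 | 55% | 0.0 | −3.2 | +3.2 |
| C | 15.4 | 12.6 | 28.0 | 55% | −2.1 | −4.9 | +2.8 |

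The share column is constant; the change in I separates the cases. Starting from T = 20, the change in I is +2.2, 0.0 and −1.2; from T = 50 it is +5.6, 0.0 and −3.0.

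**Difference of absolute changes.** The last column barely separates the cases. With a 50/50 start it equals (2s − 1) × T, that is 0.1 × T. It also misleads when the baseline split is unequal. Take T = 35 at 40/60 (14.0 + 21.0) and let both kidneys lose 20%, giving 11.2 + 16.8. The share stays at 11.2/28.0 = 40%, correctly showing no differential effect. The difference of changes is −2.8 − (−4.2) = +1.4, an apparent benefit where there is none.

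**Log-ratio contrast.** The change in ln(I/C) is 0 in the 40/60 example and ln(0.55/0.45) = 0.20 in A, B and C. Total eGFR cancels from it, so it is a rescaled split share. It is a sound between-kidney contrast, but the separate per-kidney changes are still needed to say which kidney moved.

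**Precision.** By the delta method, var(s × T) = (s × SD_T)² + (T × SD_s)². Assume a within-patient eGFR CV of 5 to 10% and a split SD of 2 to 5 points (neither is in the documents). In case A at T = 35, the SD of the change in I is then 1.7 to 3.8 against a true change of 3.9. For a mean over 30 patients the standard error is 0.3 to 0.7, counting measurement error only.

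**The case against.** The strongest reply is that the ambiguity is already resolvable. Serial creatinine and eGFR are the primary efficacy measures, and Section 14.7.3 summarises laboratory change from baseline. In the example the totals (38.9, 31.8 and 28.0 from 35) separate the cases, and Section 14.8 leaves room for further exploratory work. This stands so far as it goes: the information is not lost. But separate summaries of share and eGFR do not give per-kidney change patient by patient. If the product is left undefined, the visit pairing, baseline and kidney coding become choices made after the data are seen.

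A reader might infer that the primary question goes unanswered because neither eGFR nor the split shows whether the treated kidney stabilised. The documents do not support that. Sections 14.2 and 14.3 assess stabilisation by serum creatinine and eGFR, which is whole-patient function, and the split is one exploratory item among several.

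A reader might also infer that multiplying by eGFR gives measured absolute function with a clean concurrent control. It does not, for these reasons:

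- Section 12.4.3 says only that uptake correlates with filtration, and it permits other agents at some sites. The product carries both eGFR and scan error.
- Biopsy and injection are in the same kidney, so the effects of the procedure are mixed with those of the product.
- The change that best separates the cases, that of the injected kidney, is itself an uncontrolled before-and-after change.
- Section 11.3 does not require the baseline scan to be repeated if injection is delayed, and Section 14.7.3 takes laboratory baseline immediately before injection. Pairing at baseline is therefore not automatic.

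**Conclusion.** The concern holds for the endpoint as defined. A gain in the injected kidney's share is compatible with improvement, stability or decline of that kidney. In the illustration one 5-point gain covers changes from +3.9 to −2.1 mL/min/1.73m² in the injected kidney. The identity needs no assumption. The sizes rest on the assumed starting eGFR, the 50/50 split, the 5-point shift and the 20% fall in case C.

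The defect lies in the derived variable, not in data collection, and it does not reach the primary efficacy measures. The share remains the right between-kidney contrast because equal proportional decline leaves it unchanged; what is missing is a per-kidney level beside it. At the upper end of the assumed errors a single patient's estimate is borderline, so the supplement is mainly useful for group description. Severity is modest.

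**What to change.** Amend Sections 7.2, 14.2, 14.3 and 14.7.4 as follows.

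1. Keep the split share as the between-kidney contrast, coded injected versus uninjected instead of left versus right.
2. Add a supplementary descriptive variable: estimated single-kidney eGFR, equal to share times central-laboratory CKD-EPI eGFR from the scan visit. Use the scan-visit value at baseline too, with a stated pairing window, not the laboratory value taken immediately before injection.
3. Tabulate change from pre-injection for the injected and the uninjected kidney at Months 6, 12 and 18. Do this separately for new and previously injected patients: the latter have a post-treatment baseline, and in new patients Month 6 precedes any second injection.
4. Do not use the difference between absolute changes as the contrast. If a combined contrast is wanted, use proportional (log-ratio) change.
5. State the limits: the product is an estimate with eGFR and scan error, the agent may differ by site, the uninjected kidney is an imperfect control, and a baseline scan may precede a delayed injection. Flag such scans in the listing.

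The cost is SAP wording, a pairing rule, per-kidney derived values and one table. Scans and renal chemistry are already scheduled at the same visits, so no procedure is added.

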6.5.3 Selection of Kidney for Biopsy/Injection

Laparoscopic surgical techniques can be used to access either the right or left kidney. However, the left kidney is more readily accessible and is most often accessed during nephrectomies, hence the first surgical team had more experience with accessing the left kidney, and the initial patients enrolled underwent left kidney biopsy and left kidney NKA injection. Patients previously enrolled may have a second NKA injection in the left kidney. Newly enrolled patients may have either the left or right kidney biopsied. In any case, the NKA injection should be made into the kidney that was biopsied.

6.6Benefit: Risk Assessment

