10 STUDY POPULATION

10.1 Eligibility Criteria

Eligibility criteria should be assessed at Screening. In addition, unless otherwise noted for the specific criterion, eligibility criteria should be also be reviewed before the biopsy and at the Day -10 to -14 pre-injection visit.

Up to 30 subjects will be enrolled in this study, including subjects previously injected in either Phase 1 trial. Note that a subject will be considered enrolled into the study at the time of injection.

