12.5 Surgical Procedures

12.5.1 Biopsy

The biopsy should be collected from the left/right kidney under sterile conditions using an ultrasound or CT guided method as dictated by site standard practices. The only difference from the standard procedure may be collection of 2 tissue cores and use of a 16 gauge needle. Two biopsy renal tissue cores are needed to insure sufficient cortical tissue is collected for selection of SRC and manufacture of NKA. Likewise, a 16 gauge biopsy needle should be used to insure sufficient cortical material is collected for manufacture of NKA. If site standard practices dictate use of a 15 gauge biopsy needle, then a 15 gauge needle may be used following consultation with the Medical Monitor. In any case, it is imperative that as much cortical tissue is collected as possible. If available at the site, bedside examination of the biopsy cores may be performed to ensure sufficient cortical material is obtained.

It is important to remember that the biopsy tissue will be used to manufacture NKA, an injectable product. Therefore, the site should ensure that individuals collecting the biopsy are aware that the tissue cores must be harvested using sterile conditions so that the risk of contamination during cell expansion and selection is minimized. Product with microbial bioburden cannot be released for injection, so contamination of the tissue cores during collection could significantly jeopardize RegenMed (Cayman) Ltd.'s ability to manufacture an NKA product for that patient.

Guidance on wound care and pain management following the injection procedure will be provided in the Study Reference Manual. Importantly, pain medication administered to the patient post-biopsy should selected carefully, avoiding as possible medications with nephrotoxic potential as discussed in Section 10.2. Specialized patient care surrounding the injection will focus on minimizing potential bleeding events. The subject will remain supine for 4 hours with monitoring of hemoglobin, blood pressure, gross hematuria, abdominal/flank pain, and flank

ecchymosis. In addition, the patient may be discharged the day of biopsy per site standard practice.

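### The exploratory split-function endpoint contrasts left with right kidney, but patients may be injected on either side, so it does not identify treated versus untreated kidney

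*Combined protocol and SAP*

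**What the plan says.** The endpoint is a comparison, before versus after injection, of "split functional differences between the left and right kidney based on renal scintigraphy" (Section 14.3, repeated in Sections 7.2 and 14.2). It names anatomical sides and does not mention which kidney was treated.

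On the side of treatment, Section 6.5.3 says of the Phase 1 patients that "the initial patients enrolled underwent left kidney biopsy and left kidney NKA injection". For this trial it says "Newly enrolled patients may have either the left or right kidney biopsied" and "In any case, the NKA injection should be made into the kidney that was biopsied". Section 12.5.1 agrees: "The biopsy should be collected from the left/right kidney under sterile conditions". The Study Enrollment paragraph of the synopsis ties every injection to the biopsied kidney without naming a side, and the first part of Section 9 allows a biopsy on either side.

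Two places keep left-only wording. Later in Section 9 the patient is to "receive an NKA injection into the left (i.e., biopsied) kidney", and Section 8.3 refers to the left kidney when it states the maximum injected volume.

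On analysis, Section 14.7.4 puts scintigraphy in a data listing and leaves descriptive statistics to be produced if they seem useful. Section 14.6 (Efficacy Analysis) is marked as not applying. The subgroups in Section 14.8 are one versus two injections and laparoscopic versus percutaneous route; there is none by injected side.

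**The concern.** In a single-arm trial in which one kidney is treated, the untreated kidney of the same patient is a useful concurrent comparator. Serum creatinine and eGFR reflect both kidneys together and cannot provide that comparison. Split scintigraphy can, because it assigns a share of function to each kidney at the same time point, and the schedule for new patients has it before injection and at 6, 12 and 18 months.

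The comparison works only if it is oriented by treatment. A left-minus-right difference moves one way when a left kidney benefits and the opposite way when a right kidney benefits. Averaged over a mix of sides, the two partly cancel. A real effect on the injected kidney could then look small or absent, for a reason that has nothing to do with the product. If the orientation is chosen only after the data have been seen, the choice becomes post hoc.

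**Working it through.** The plan gives no effect size, standard deviation or sample size calculation for this endpoint, so there is no figure to reproduce. The check is algebraic.

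**Inputs from the documents**

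- Maximum number injected: 30, including returning patients (Section 10.1: "Up to 30 subjects will be enrolled in this study, including subjects previously injected in either Phase 1 trial").
- Patients already injected in Phase 1: 7 (Section 6), on the left (Section 6.5.3).
- Side in new patients: left or right (Sections 6.5.3, 9 and 12.5.1).

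**Assumptions, not in the documents**

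- All 7 earlier patients return and the maximum of 30 is reached, so 30 − 7 = 23 are new.
- A proportion p of new patients is injected on the right.
- The effect on the injected kidney is the same in every patient.

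**Step 1: one patient.** Let D be the change in the contrast injected minus contralateral. The left-minus-right contrast then changes by +D if the left kidney was injected and by −D if the right was.

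**Step 2: pooled mean.** With a proportion q of all patients injected on the right:

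(1 − q)(+D) + q(−D) = D(1 − 2q)

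**Step 3: by number injected on the right, out of 30.** The fraction kept is 1 − 2k/30.

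| Right-injected, k | Fraction of D kept |
|---|---|
| 0 | 1.00 |
| 3 | 0.80 |
| 5 | 0.67 |
| 8 | 0.47 |
| 10 | 0.33 |
| 15 | 0 |
| 16 | −0.07 |

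**Step 4: expected fraction with 7 returning and 23 new patients.** Here q = 23p/30, so the fraction is (7 + 23(1 − 2p))/30.

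- p = 0.10: (7 + 18.4)/30 = 0.847
- p = 0.25: (7 + 11.5)/30 = 0.617
- p = 0.50: (7 + 0)/30 = 0.233

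If no earlier patient returns and all 30 are new, the fraction is 1 − 2p, which gives 0.80, 0.50 and 0. Fewer returning patients therefore means more dilution at the same p.

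**Step 5: how likely is reversal?** It needs at least 16 of 30 injected on the right. If side is treated as an independent draw in each of 23 new patients, the binomial probability is about 0 for p = 0.10 or 0.25, and 4.7% for p = 0.50. With 30 new patients and p = 0.50 it is 43%.

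**Step 6: after re-orientation.** With injected minus contralateral as the contrast, each patient contributes +D and the fraction is 1.00 whatever the mix of sides.

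**The case against.** The strongest reply is that the harmful analysis is not in the plan. No section prescribes a pooled, signed left-minus-right mean. Scintigraphy goes into a listing with optional descriptive statistics, the endpoint wording gives no sign, and an analyst who knew the side could orient the data by treatment. This stands as a limit: the loss occurs only if the endpoint is summarized as worded. It does not remove the defect, because the stated contrast is by anatomical side in all three places and nothing elsewhere replaces it.

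Four stronger readings are tempting but not supported:

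- **That the endpoint is likely to show the wrong sign.** If 75% of 23 new patients were injected on the right, the expected fraction would be (7 − 11.5)/30 = −0.15. Nothing in the documents suggests a right-sided majority, and Section 6.5.3 calls the left kidney easier to reach laparoscopically. Dilution is the realistic concern.
- **That scintigraphy is the only within-patient concurrent control.** MRI and ultrasound also image both kidneys (Section 12.4), and MRI may be used for cortical thickness. What can be said is that split scintigraphy is the scheduled functional measure that separates the kidneys.
- **That the wording was carried over from Phase 1.** It would fit left-only injection, but the description of Phase 1 in Section 6.3.4 gives its renal-function objective in terms of laboratory assessments and mentions no split-function endpoint.
- **That the MRI volume endpoint has the same fault.** It compares volume before and after injection and contains no left-right contrast.

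The common-effect assumption is also a simplification. Returning patients have a pre-injection scan that follows a previous injection and receive one more, while new patients may receive two.

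**Conclusion.** The point holds as a definition problem. The endpoint is stated by anatomical side, treatment is not, and no rule connects the two. If it is summarized across patients as worded, the fraction of the injected-kidney effect kept is 1 − 2q: about 85%, 62% or 23% when 10%, 25% or 50% of 23 new patients are injected on the right and 7 left-injected patients return. Those percentages, the number returning and the full enrollment of 30 are assumptions. With every injection on the left there is no loss. Full cancellation needs 15 of 30 on the right, and reversal needs more.

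The consequence is confined to an exploratory, descriptive endpoint; primary and secondary outcomes are untouched. It is still worth correcting before data are seen, because the remedy is small and the within-patient comparison is informative in a trial without a control group.

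**What to change.** In Sections 7.2, 14.2 and 14.3, define the endpoint as the change from pre-injection in the injected kidney's share of total function on scintigraphy (injected versus contralateral).

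In Section 14.7.4, commit to a descriptive summary in that orientation, alongside the listing.

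Confirm that the case report form captures the injected side, and add a field if it does not. Section 14.7.1 lists biopsy and injection data but does not name side among them.

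Reconcile the left-only wording in Section 8.3 and the later part of Section 9 with the Study Enrollment paragraph of the synopsis, Section 6.5.3, the earlier part of Section 9 and Section 12.5.1. Which rule applies is for the sponsor and investigators to settle.

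The cost is a few sentences, one derived variable and at most one form field. No visit or procedure is added.
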